2.2 Vitamin D Intervention

Aim 2: To identify shifts in the composition of the human microbiome and CRC risk factors specifically caused by the consumption of Vitamin D supplements.

IRB # 1845028-2 Version 3

Vitamin D is one of 4 fat-soluble vitamins that are only obtained from dietary or supplementary intake, and which is necessary for healthy immune function, bone metabolism and electrolyte absorption.⁸⁻¹¹ Since the 1980's intake vitamin D containing foods, milk, eggs, fish and mushrooms has been declining in the United States. 12 Most concerning has been the sharp decline in consumption of cow's milk, which is a primary source of vitamin D, particularly among young females. 13 Unfortunately, there has also been a sharp rise in EOCRC since 2000, from a rate of 5.9 cases/100,000 to 8.5 in 2018 (SEER). Projections for 2030 suggest 23% of rectal and 11% colon cancer will be diagnosed in US adults under the age of 50.14 Recently, however, a study using incident cases of EOCRC from the Nurses' Health Study II, demonstrated a 50% reduced risk of EOCRC from total dietary intake of vitamin D >/= 450 IU/day vs <300 IU/day (HR = 0.40, 95% CI, 0.26-0.93).¹⁵

Recent studies have determined the impact of habitual vitamin D intake and vitamin D supplementation on the human microbiome, and demonstrated beneficial modifications in composition. 16 Specifically, 12 weeks of weekly oral dose of 50,000 IU vitamin D₃ in 80 women increased the Bacteroides/Firmicutes ratio and increased probiotic bacteria Akkermansia and Bifidobacterium. 16 It is yet unclear mechanistically how Vitamin D alters the composition and function of the microbiome, but several lines of evidence indicate a bi-directional interaction. Indirect effects of Vitamin D on the microbiota include systemic effects through the vitamin D receptor (VDR), which is expressed not only in the proximal colon but also functions as a transcription factor in a large number of genes that control immune response. 17,18 Likewise. specific bacteria influence VDR expression in host cells. 19,20

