In addition to vitamin D intake, the gut microbiome structure and function is also a significant risk factor for CRC development. Multiple studies demonstrate significant loss of diversity, and increases in pathogenic bacteria, Fusobacterium nucleatum and Bacteroides fragilis, are risk factors for CRC development and progression. Recent preliminary data using data from The Cancer Genome Atlas, demonstrated a distinct intra-tumor microbial composition in EOCRC vs late-onset, along with positive association between T regulator cells and inflammasome pathway.²¹ Thus, it is possible that the vitamin D insufficiency or deficiency may be also affecting gut microbiome structure and function negatively, increasing EOCRC risk.

Although dietary vitamin D supplementation has been used in the clinical setting for decades, the effect of supplementary vitamin D consumption on the structure of the microbiome has not been studied in humans in fine scale or with concomitant adjustment for dietary intake. Understanding the interaction of vitamin D with the microbiome in humans could lead to important advancements in the understanding of how vitamin D together with diet impacts the microbiome composition, and ultimately, risk of EOCRC. This study has the potential to lay the ground work for an adjunctive therapy to manipulate the microbiome to reduce risk of EOCRC. This proposed study is designed to evaluate the effect of vitamin D supplementation on the normal structure of the microbiome and data will not be used to diagnose, prevent, cure or treat disease.

IRB # 1845028-2 Version 3 Date: March. 3 2022

3 **Experimental Design**

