Study participants will complete 16 days of active study involvement after providing informed consent on day 0, which will be conducted over a period of 12 weeks. There will be 4 in-person visits, including the consent visit where the participants will have contact with the researchers. Visit 1 will be the consent visit and participants who consent will receive training on how to collect stool samples, take supplements and dietary record keeping with an online diet record tool called ASA24. Visit 1 will include a fasting blood draw and body composition measurement. At visit 1 participants will receive stool collection kits for week 1 and their supply of dietary intervention supplements (gummies) as well as written instruction on how many gummies to take each day during the intervention period. They will also complete a food frequency questionnaire, the DHQIII online. At visit 2 participants will receive collection kits for week 2 and their supply of dietary intervention gummies as well as written instruction on how many gummies to take each day during the intervention period. At study visit 3, participants will complete a fasting blood draw, stool kit for Study day 16, and intervention gummies. At visit 4, this will conclude the study. Participants will complete a fasting blood draw, body composition measurement, dietary recall and mental health survey. The process for returning fecal samples is described below in Section 6.2.

3.1 **Study Outline**

Study Day 0 (Study Visit 1)

- Fasted blood draw
- Body composition
- DHQIII online
- Stool history
- Mental health questionnaires

Study Days 1-14

- Consume vitamin D or placebo as gummies for 14 days
- Consume normal diet and keep detailed dietary records using ASA24 (daily 24-hour recalls)
- Collect 1 stool sample per day for 14 days
- Study Visit 2/Study day 7 delivery of 2nd week of stool collection kits

Study Day 15 (Study Visit 3)

- Fasted blood draw
- Provide vitamin D or placebo gummies to last through week 9
- Stool history
- Post self-perceived stress scale

Study Day 16 (Study Visit 4)

- Provide remainder vitamin D or placebo gummies to last through week 12
- Provide stool collection kit for Study day 16

IRB # 1845028-2

Study Day 16 (Study Visit 5)

- · Fasted blood draw
- Stool history
- ASA24 dietary record
- Body composition
- Collect final stool sample
- Post self-perceived stress scale
- Global Physical Activity Questionnaire (GPAQ)

Visit/Intervention Schedule 3.2

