Study Visit Number	1							2								3	4	5
Study day (0-15)	0	1	2	3	4	5	6	7	8	9	10	11	12	13	14	15	16	17
Week of study	1	2						2							3			12
Decide if you want to participate	✓																	
Study training	✓																	
Study checkup								>								>	>	✓
Complete questionnaires	✓															√	✓	1
Measure body composition	✓															✓		✓
Collect stool		✓	1	✓	✓	✓	✓	✓	✓	✓	✓	✓	✓	✓	✓			✓
Record diet		✓	✓	✓	✓	✓	✓	✓	✓	✓	✓	✓	✓	✓	✓			1
Take dietary supplement		✓	√	✓	✓	√	✓	✓	✓	✓	1	✓	✓	1	✓	✓	✓	✓
Fasting blood draw	✓															✓		✓

Statistical Design and Microbiome Analysis 4

This longitudinal study will allow for the use of each subject as their own control. We will perform testing for associations between diet, taxa, groups of bacterial taxa (and their functional capacities) with metadata parameters in different combinations. We will test the null hypotheses that there are no associations between dietary intake variability and microbiome composition within and between subjects, and between dietary intervention groups. Finally, we will test the null hypothesis that vitamin D has no effect on the microbiome.

IRB # 1845028-2 Version 3 Date: March, 3 2022 **Primary Outcome:** Microbiome composition and the relationship with dietary and supplemental intake of vitamin D and serum vitamin D levels

Secondary Outcomes: Circulation inflammatory markers (e.g. TNFα, IL-8, CRP); markers of gut permeability (e.g. zonulin, intestinal fatty acid binding protein, soluble CD14, lipopolysaccharide and lipopolysaccharide-binding protein); glucose and insulin; and other nutritional and microbial metabolites.

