4.1 Sample Size

We will enroll 40 adults in this study. The adults will be randomized, with 20 individuals per study arm, to receive either vitamin D (4000 IU daily) or placebo during the intervention period. To control for initial vitamin D (25(OH) D3) levels at baseline (including those with hypovitaminosis), subjects will be randomized using 1:1 matching based on vitamin provided from blood samples at study visit 1. Study PI will be blinded to subject randomization. We will obtain 15 stool samples and 15 24-hour dietary recalls from each individual, for a total of 561 stool samples and 561 dietary records. We will obtain pre- and post- intervention blood samples from each individual for a total of 81 blood samples. We performed a power analysis using vitamin D as the primary exposure, and the top 10 dominant microbial taxa as the primary outcome. Using monte carlo simulation of microbial taxa distributed according to a lognormal distribution, and a non-parametric Mann-Whitney U test for significant differentiation, we found that this sample size is sufficient to detect a change of ≥ 1.24 standard deviations in any one of the dominant taxa. This analysis accounted for multiple hypothesis testing using Bonferroni correction.

5 Participant Selection

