6.8 Microbiome Analysis

We will use RNA gene sequencing or 16S gene amplicon sequencing or shotgun DNA sequencing as well as novel methods in development relying on sequencing a subset of the fecal microbial RNA or DNA to accurately characterize taxonomic composition of the microbiome.

7 Participant Withdrawal

Participants may withdraw voluntarily at any time.

Participants may be withdrawn from the study by the PI for the following reasons:

- The participant is diagnosed with a disease that may affect their ability to pass feces.
- The study is stopped.

If a subject withdraws from the study, no further data will be collected on the subject. The data that have been collected to that point will continue to be used unless the subjects notifies the PI.

8 Assessment of Safety

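### Section 7 lets the PI remove a randomised participant for a new bowel-related diagnosis and, on the natural reading, ends all collection, so the week-12 blood draw is lost for a reason that concerns stool (minor)

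*Combined protocol and SAP*

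**What the plan says.** Section 7 (Participant Withdrawal) allows voluntary withdrawal at any time and lists two grounds on which the PI may withdraw someone. One is that the study stops. The other is "The participant is diagnosed with a disease that may affect their ability to pass feces". Nothing limits this ground to the time before randomisation. The section then states "If a subject withdraws from the study, no further data will be collected on the subject", followed by "The data that have been collected to that point will continue to be used unless the subjects notifies the PI". It does not separate stopping stool collection or the supplement from leaving the study, and it has no separate rule for PI removals.

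Sections 3.1 and 3.2 place fasting blood draws at day 0, day 15 and the final week-12 visit. Stool is collected daily on days 1 to 14, and the last visit adds one item, "Collect final stool sample". The two sections number that visit differently, but both give it a fasting draw and the schedule puts it at week 12.

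Section 4 makes serum vitamin D part of the primary outcome. Its secondary outcomes include circulating inflammatory markers, glucose and insulin, and "markers of gut permeability (e.g. zonulin, intestinal fatty acid binding protein, soluble CD14" among others.

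**The concern.** The ground for removal is about stool, but the consequence reaches everything else scheduled: blood, body composition, diet record and questionnaires. Aim 2 in Section 2.2 asks about shifts in the microbiome and in "CRC risk factors specifically caused by the consumption of Vitamin D supplements". That is a causal question, and it rests on comparing the arms as randomised.

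A bowel disease diagnosed during the 12 weeks arises after randomisation and may be related to inflammation or gut permeability, which are among the outcomes. Ending blood collection because of it creates missing data that could have been avoided and that may depend on the values not observed. What is at stake is the week-12 blood comparison. The primary taxa analysis is less affected, because the stool itself may be unobtainable.

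**Working it through.** The plan gives no figure for this point. The detectable difference in Section 4.1 concerns dominant taxa and does not bear on the blood outcomes, so it is not used here.

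**What a removal loses**

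| Time of removal | Kept | Lost |
|---|---|---|
| Days 1–14 | Day-0 blood; stool and diet records so far | Day-15 and week-12 blood; remaining stool and records |
| After day 15, before the last visit | Day-0 and day-15 blood (2 of 3 draws); up to 14 of 15 planned stool samples | The only week-12 blood draw; final stool, body composition, diet record, questionnaires |

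**Is there any other follow-up rule?** Section 12.2 seeks vital status, but only after a participant revokes authorisation to use health information. Section 6.2 tells participants who pass no stool on a given day to skip the sample, return the kit empty and keep recording diet. That is a proportionate response to missing stool, and Section 7 does not carry it over to a PI removal.

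**Size at week 12.** Inputs: 20 per arm (Section 4.1); the number of diagnoses is an assumption, since no rate is given.

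- Share lost: 1/20 = 5% of an arm per removal.
- Precision, in outcome SD units: the standard error of the arm difference goes from sqrt(1/20 + 1/20) = 0.316 to sqrt(1/19 + 1/20) = 0.320, a rise of about 1%.

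**Illustration of selective loss.** Assume no true effect and that those lost are the most extreme in their arm on a latent variable with correlation r to the outcome. With one lost from one arm only, the expected extreme of 20 standard normals is 1.867, so the shift is r × 1.867 / 19. At r = 0.5 this is 0.5 × 1.867 / 19 = 0.049 SD. Simulation with 200,000 replicates agrees and gives the other cases:

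| Losses by arm | r = 0.3 | r = 0.5 | r = 0.7 |
|---|---|---|---|
| 1 v 1 | 0.00 | 0.00 | 0.00 |
| 1 v 0 | 0.030 | 0.049 | 0.070 |
| 2 v 1 | 0.025 | 0.042 | 0.059 |
| 2 v 0 | 0.054 | 0.090 | 0.127 |

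At r = 0.5, one loss on one side is 0.049 / 0.320 = 15% of the standard error. Two losses on one side are 0.090 / sqrt(1/18 + 1/20) = 0.090 / 0.325 = 28%.

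If two diagnoses occurred unrelated to arm, the chance that both fall in the same arm is 2 × C(20,2) / C(40,2) = 380/780 = 0.487. Either arm is equally likely to be the one affected, so the expected bias is zero.

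**Cost of retention.** A retained active-arm participant with no supplement effect shrinks the mean contrast by 1/20 = 5%; with half the effect, by 2.5%. If the disease itself moves a marker by 1 to 3 SD (an assumption), that arm's mean moves by 1/20 to 3/20 = 0.05 to 0.15 SD.

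**The case against.** The strongest reply is that this is a mechanistic study in healthy adults. Section 2.2 says it will "evaluate the effect of vitamin D supplementation on the normal structure of the microbiome", and Section 5.1 excludes people with inflammatory bowel disease, heart disease or diabetes from the whole study, blood included. A new bowel disease could disturb the blood markers directly, so removal has a rationale. This supports stopping stool collection, or leaving later stool out of the taxa analysis. It does not carry over to blood: an entry criterion defines who is randomised and does not justify dropping a randomised participant for a later event that may relate to the outcomes.

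Several narrower objections stand. Removal is discretionary, so the PI can retain an affected participant under the present text. The word used is withdraws, and the next sentence depends on the participant notifying the PI, so the rule may have been written for voluntary exits; Section 7 would then be silent on PI removals and still need a sentence. The day-15 draw and nearly all stool are kept. Section 4 does not say whether the permeability markers are assayed in blood, so they are not counted among the certain losses. The selective-loss figures need one-sided loss of the most extreme participants, and nothing in the documents supports that. Retention brings chance imbalance of a similar size.

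A reader might infer that the rule biases the arm comparison. The documents do not show that. Section 4.1 states "Study PI will be blinded to subject randomization", which limits differential removal, and balanced loss produces no shift in the illustration.

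**Conclusion.** The point holds as a minor one. On its natural reading, Section 7 turns a problem with stool into the loss of a scheduled week-12 blood draw, and no other section provides follow-up after a PI removal. The certain losses are circulating inflammatory markers, glucose, insulin and serum vitamin D at week 12.

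Each removal costs 5% of an arm at that visit. In the illustration, one-sided loss of one or two extreme participants shifts the null difference by about 0.03 to 0.13 SD, with zero expected bias if diagnoses are unrelated to arm. Bias needs losses, or their relation to outcome, to differ by arm. Few such diagnoses are likely in 40 adults over 12 weeks, though that is a judgement because no rate is given.

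A reader might also infer a loss of power for the primary taxa analysis that the change would repair. That is not supported: most stool is already in hand by day 14, and the final sample may be unobtainable anyway. The gain is recovered blood data and less informative missingness.

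**What to change.** In Section 7, confine the stop on collection to participants who withdraw consent for follow-up. For the bowel-disease ground, write along these lines:

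> Stool collection stops where needed, as under the skip rule in Section 6.2. The participant is invited to the remaining scheduled visits for fasting blood, body composition, diet record and questionnaires, and for the final stool if obtainable. The date and reason are recorded.

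Analyse blood outcomes by randomised arm, with a sensitivity analysis that excludes data after the diagnosis. Flag any stool given after the diagnosis; whether it enters the taxa analysis is for the investigators, given the healthy-microbiome target. Whether the supplement continues is a clinical decision.

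The cost is an amendment and consent wording, since the visits and draws are already scheduled and attendance stays voluntary. The statistical downside is dilution of up to 5% of the arm contrast per retained active participant with no effect if the supplement was stopped, and added noise if the disease itself shifts the markers. The sensitivity analysis shows how far either matters.

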8.1 Safety of biological sample collection

Collecting fecal samples is a low risk procedure. Fecal collection kits will contain gloves for participants to wear while collecting their own samples when the chance of contact with stool is highest. The sampling kit contains ammonium sulfate, and participants will be instructed not to ingest this substance. Participants will be instructed to wash their hands thoroughly after completing each stool collection.

Fasting blood draws a generally considered minimal risk procedures. There is a small risk of pain and discomfort during the blood draw and it is possible that bruising at the site of the draw will occur.

8.2 Safety of dietary supplement intervention

Vitamin D occurs naturally in low amounts in foods, including cow's milk, fish, eggs and mushrooms. Most commercially available vitamin D supplements are made from processing sheep wool to extract lanolin. This product is then saponified and refined using solvent washes. This crude cholesterol is then subjected to a series of chemical reaction to produce 7-dehydrocholestrol, which is then exposed to UV light to form vitamin D3. The upper limit of

IRB # 1845028-2 Version 3 15

vitamin D intake as set forth by the Institute of Medicine and USDA is 4000 IU/day for adults over 19. Safety testing for various doses of vitamin D has been previously conducted in healthy adults at 3 doses, 400, 4000, and 10,000 IU/day, with 4000 IU dose produce milder hypercalcemia in 3% of subjects (N=373) ages 50-70.²³ Thus, this does has been deemed safe in adults for long-term intake.

9 Potential Benefits

Subjects will not personally benefit from giving specimens. The results are not expected to be clinically meaningful to the study participants. The research will benefit the larger research community by enabling the development of better methods to relate dietary intake to the microbiome.

Participants may request an electronic information packet with their individual results via email. Results will include the composition of their gut (most abundant taxa) as well as other relevant individual markers and summary information of dietary intake. To maintain confidentiality, personalized information packets will be sent (at the completion of the course associated with this study) by the study PI. Also included in this informational packet will be a comparison of that individual's microbial community to those of other study participants, in de-identified aggregate. This may include a graphical representation of ecological distance to other patients, comparison diversity scores, and other summary statistics. This will be accompanied by a disclaimer that this information should be used for research purposes only and is not a reliable clinical test for any purpose. Participants will be notified via email upon completion of the study of this information's availability upon request.

10 Study Timeline/Duration

Recruitment for the study will begin during January 2022 with the data collection completed by December 2022.

11 Data Management

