The recommended dose of vitamin D for adults is 600 IU/day and has an upper limit of 4000 IU/day, with clinical intervention to replete deficiency being 50,000I IU/day. We have set our dose at the upper daily limit, established by the Institute of Medicine, since this study is not mean to replete a clinical deficiency. The supplement will be provided as Nordic Naturals vitamin D3 gummies, which have been certified by a third party with Good Manufacturing Procedures. For these gummies, 4 gummies will provide 4000 IU of vitamin D3. Subjects will consume 4 gummies at the largest meal of the day for 12 weeks. Subjects who are assigned to the placebo group will be provided with placebo gummies, Yum Earth Organic Vegan Fruit Snacks, which have the same composition as the supplement but no vitamin D3. Both will be put in bottles without manufacture labeling so as to disguise the vitamin D from placebo. If for any reason we are not able to get these placebo products, we have the ability to print 3D molds and make our own placebo gummies, which we have done before in our food lab. See Table 1 for list of ingredients.

Table 1. Ingredients list of vitamin D3 and placebo supplements							
	Vitamin D	Placebo					
Ingredients	vitamin D (cholecalciferol)	Organic rice syrup					
	Organic tapioca syrup	Organic cane sugar					
	Organic cane sugar	Pectin					
	purified water	Citric Acid					
	pectin	Ascorbic Acid					
	citric acid	Natural flavors colored with					
		organic concentrate (Apple,					
		carrot,					
		pumpkin,blackcurrent)					
	furamic acid	Organic sunflower oil					
	natural flavor	Organic carnauba wax					
	sodium citrate dihydrate						
	fruit and vegetable juice (color)						
Allergens	Gluten Free	Vegan					
	Contains milk derivatives	Gluten Free					
	Non-GMO	Non-GMO					

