6.6 Blood Draw

Blood will be drawn by a licensed phlebotomist from a peripheral arm vein at the designated visits through standard sterile methods. At each blood draw, ~15mL of blood of blood will be collected. Participants will be asked to fast for at least 8 hours prior to the blood draw. Participants will remain in a seated position throughout the procedure and be observed for light-headedness, bleeding, and bruising before, during, and after the procedure. If a participant experiences light-headedness they will be given the option to recline or lay down and continue to be monitored until the light-headedness resolves. If the phlebotomist is unable to successfully locate a vein after three attempts, the blood draw will not be completed.

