11.2 Monitoring Plan

This is a minimal risk trial. Data will be monitored by the PI. Sample acquisition carries minimal to no known medical risk to the subjects. The nature of risk for accessing private records will be minimal to none, since all data collected will be de-identified. Possible invasion of privacy may occur as other participants may observe the fecal specimen being dropped off. Interviews will be conducted in private rooms or sectioned-off areas in order to maintain privacy of our participants. Participant data will be de-identified. As a result of the de-identification process, individuals participating will be assigned a unique identifier number. This unique identifier will be used to link de-identified samples and data collected from the interview (data listed in the Data Collection section). Study coordinators will have access to the link during the data collection period. The study PI will only have access to the link to the unique identifier after the course completion to protect the identity of student study participants during the course. The identifiers will be maintained in a database on a secure computer protected with password access and full-disk encryption. If a breach in confidentiality occurs, we will report the breach to the Institutional Review Board (IRB) and the HIPPA Privacy Officer as per institutional policy.

12 Administrative Considerations

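### The protocol cites 3% mild hypercalcaemia at the study dose but names no serum calcium measurement and no other safety monitoring of the supplement

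*Combined protocol and SAP*

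**What the plan says.** Section 8.2 refers to safety testing of three daily doses (400, 4000 and 10,000 IU) and reports "4000 IU dose produce milder hypercalcemia in 3% of subjects (N=373) ages 50-70". It then concludes that the dose is safe for long-term use in adults.

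That is the dose used here. Under Section 4.1 participants are randomised, "with 20 individuals per study arm", to "receive either vitamin D (4000 IU daily) or placebo during the intervention period". The Dietary Supplement Intervention section (6.4) adds: "Subjects will consume 4 gummies at the largest meal of the day for 12 weeks". Section 5.1 admits anyone aged 18 or older.

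On blood, the schedule in Section 3.2 has a row "Fasting blood draw" marked at day 0, day 15 and the final visit in week 12. Section 6.6 gives the volume, "At each blood draw, ~15mL of blood of blood will be collected", and lists no analytes. The analytes appear in the outcomes of Section 4: serum vitamin D, inflammatory markers, gut-permeability markers, and "glucose and insulin; and other nutritional and microbial metabolites".

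On oversight, Section 11.2 states "This is a minimal risk trial. Data will be monitored by the PI" and then discusses sample acquisition, access to records and privacy. Section 7 gives two grounds on which the PI may withdraw a participant: a disease affecting the ability to pass feces, and the study being stopped.

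**The concern.** Mild hypercalcaemia is a laboratory finding, and it will usually go unseen unless calcium is measured. The protocol puts a number on this effect at its own dose, draws suitable blood before, during and at the end of exposure, and then does not name the assay. Nor does it describe any other way in which a supplement effect would come to notice.

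Two things are at stake. An individual participant with raised calcium might not be identified. And a later report that no safety problem was seen would rest on never having looked, in a population that reaches well below the ages of the cited data.

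**Working it through.** **1. Where could calcium be measured or a harm be recorded?**

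| Place | Content bearing on supplement safety |
|---|---|
| Section 4, outcomes | Calcium not named; the closing category of other nutritional metabolites is open-ended |
| Section 6.6 | Volume and procedure only; no assay |
| Section 3.2 schedule and Section 6.7 | A checkup row, and optional contact to check on progress; neither is said to collect adverse events |
| Section 7 | No laboratory criterion |
| Section 8.2 | Cites the 3%; describes no measurement |
| Section 11.2 | PI monitoring; no safety laboratory test or adverse-event collection |

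Elsewhere, the word calcium occurs only in a reference title.

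**2. The cited figure.** The 3% is a literature rate, so there is no calculation to reproduce. The text does not say whether 373 is the 4000 IU group or all three dose groups together. If it is the denominator, 0.03 × 373 = 11.2, or about 11 cases. If one third of it is (an assumption), 373/3 ≈ 124 and 0.03 × 124 = 3.7, or about 4 cases.

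**3. Expected cases among 20 exposed, if 3% applied.**
- Expected number: 20 × 0.03 = 0.6.
- Chance of at least one: 1 − 0.97^20 = 0.456.
- Chance of at least two: 0.120.
- Chance of at least one with incomplete follow-up: 1 − 0.97^18 = 0.422 with 18 assessed, and 1 − 0.97^16 = 0.386 with 16.

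**4. Range from the uncertainty in the 3%.** Exact 95% intervals for the rate are carried through 1 − (1 − p)^20:

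| Assumed source data | 95% interval for rate | Chance of at least one in 20 |
|---|---|---|
| 11/373 | 1.5% to 5.2% | 26% to 66% |
| 4/124 | 0.9% to 8.1% | 16% to 81% |

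This range covers sampling error and the unclear denominator. It does not cover the differences in age and possibly in duration of exposure, because the documents give no rate for younger adults and no duration for the cited study.

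**5. What 20 exposed participants can show.**
- If calcium were measured and no case seen, the one-sided 95% upper limit would be 1 − 0.05^(1/20) = 13.9%, more than four times the cited rate.
- For an 80% chance of seeing at least one case at 3%, ln(0.20)/ln(0.97) gives 53 exposed participants. For 95%, ln(0.05)/ln(0.97) gives 99.

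**6. Number of draws.** The schedule implies 40 × 3 = 120 samples. Section 4.1 plans pre- and post-intervention samples, 40 × 2 = 80, and states a total of 81. The two do not match.

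**The case against.** The strongest reply is that this is an omission and not a contradiction. Section 8.2 promises no calcium measurement, Section 4 lists scientific outcomes, and Section 11.2 sits under Data Management, where attention to samples and privacy is natural. That is correct. A reader might infer that these sections conflict with one another; they do not. They leave a gap between them.

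A reader might also infer that the harm could never be detected. The documents do not support that. The metabolite category is open-ended and could include calcium, and Section 6.6 does not limit what may be assayed. What can be said is that no measurement is planned for the purpose. Consent pages were not available, so participant-facing risk wording cannot be judged.

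Third, the dose does not rest on the cited trial alone. The Dietary Supplement Intervention section and Section 8.2 both rely on the Institute of Medicine upper limit. This is a fair point about the choice of dose, which is not questioned here. It does not supply a measurement.

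Fourth, the 46% is fragile, and 20 people cannot separate a supplement effect from background, for which the documents give no rate. This stands, and it limits what the added assay may be claimed to achieve. It does not remove the case for identifying an individual with an abnormal result.

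Finally, the protocol plans no safety conclusion. That is also true, but Section 8.2 already takes a position on safety, and a report that is silent on calcium could easily be read as reassurance.

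**Conclusion.** The point stands as an inexpensive improvement. The protocol quantifies one harm of the supplement, at the dose it gives, and contains no planned means of detecting it.

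Its size is modest and uncertain: 0.6 expected cases and about a 46% chance of at least one among 20 exposed, with a range of roughly 16% to 81%. These figures assume that a rate from people aged 50 to 70 carries over to adults of 18 or older taking the supplement for 12 weeks, and that all 20 are assessed.

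The gain from measuring is that individual cases can be found and the report can say truthfully what was looked for. It is not an estimate of the rate, and nothing here shows the dose to be unsafe.

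**What to change.** - Name serum calcium among the analytes run on the fasting blood already scheduled.
- Report it descriptively by arm, and state that a trial with 20 exposed participants cannot establish safety.
- Bring Sections 4, 8.2 and 11.2 into line, so that the harm cited in one is covered by the measurements and monitoring in the others.
- Reconcile the number of blood draws: 81 samples in Section 4.1 against three draws per participant in the schedule.

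The cost is at most 40 × 3 = 120 routine assays, with no extra visit or needle-stick. A route for handling results is also needed. Under Section 11.2 the PI has no access to the identity link until the course is complete, although study coordinators have it during data collection. How a result is acted on is for the investigators and the IRB; no threshold or clinical rule is proposed.
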